4.3.1. Potential for Photosensitivity

Patients will be advised to report any reaction to sun exposed skin. In addition, special precautions will be taken to limit any potential photo irritation effect, by minimizing the patients' exposure to light including high intensity ultraviolet B (UVB) light sources such as tanning beds, tanning booths and sunlamps. Patients may wish to limit exposure to the sun and should be encouraged to apply sunscreen/sunblock daily.

4.4. Sponsor's Qualified Medical Personnel

The contact information for the sponsor's appropriately qualified medical personnel for the study is documented in the study contact list located in the team SharePoint site.

To facilitate access to appropriately qualified medical personnel on study-related medical questions or problems, patients are provided with a contact card. The contact card contains, at a minimum, protocol and investigational product identifiers, patient study numbers, contact information for the investigator site, and contact details for a contact center in the event that the investigator site staff cannot be reached to provide advice on a medical question or problem originating from another healthcare professional not involved in the patient's participation in the study. The contact number can also be used by investigator staff if they are seeking advice on medical questions or problems; however, it should be used only in the event that the established communication pathways between the investigator site and the study team are not available. It is therefore intended to augment, but not replace, the established communication pathways between the investigator site and the study team for advice on medical questions or problems that may arise during the study. The contact number is not intended for use by the patient directly, and if a patient calls that number, he or she will be directed back to the investigator site.

5. STUDY TREATMENTS

For the purposes of this study, and per International Conference on Harmonisation (ICH) guidelines, investigational product is defined as a pharmaceutical form of an active ingredient or placebo being tested or used as a reference/comparator in a clinical trial, including a product with a marketing authorization when used or assembled (formulated or packaged) in a way different from the approved form, or when used for an unapproved indication, or when used to gain further information about an approved use (ICH E6 1.33).

For this study, the investigational products are PF-06873600, letrozole, and fulvestrant.

5.1. Allocation to Treatment

Dose level allocation will be performed by the sponsor after patients have given their written informed consent and have completed the necessary baseline assessments. The site staff will fax or e-mail a complete Registration Form to the designated sponsor study team member or designee. The sponsor will assign a patient identification number and supply this number to the site. The patient identification number will be used on all study-related documentation at the site.

No patient shall receive investigational product until the investigator or designee has received the following information in writing from the sponsor:

- Confirmation of the patient's enrollment;
- Specification of the dose level for that patient (and Arm in Part 2) and;
- Permission to proceed with dosing the patient.

The sponsor or designee will notify the other sites of the inclusion of a new patient, and will inform study sites about the next possible enrollment date.

5.2. Patient Compliance

Fulvestrant will be administered by the appropriately designated study staff at the investigational site. PF-06873600 tablets and letrozole will be distributed to the patient by the appropriately designated study staff at the investigational site.

Patients will be required to return all unused study treatment at the beginning of each cycle. The number of tablets returned by the patient will be counted, documented, and recorded.

A patient diary will be provided to the patients to aid in patient compliance with the dosing instructions. The diary will be maintained by the patient to include missed or changed PF-06873600 doses. Patients will be required to return all bottles of PF-06873600 every cycle. The number of PF-06873600 tablets remaining will be documented and recorded at each clinic visit or Day 1 of each cycle. The patient diary may also be used to support this part of the accountability process. The information above, regarding diary completion,

requirement to return all bottles and accountability documentation will also be performed on patients receiving letrozole (where applicable).

Letrozole and fulvestrant will be administered in accordance with the package insert (or equivalent). All PF-06873600, letrozole, and fulvestrant administration will be documented on the corresponding investigational product administration CRF.

5.3. Investigational Product Supplies

PF-06873600, letrozole, and fulvestrant will be supplied by Pfizer. Study centers will receive PF-06873600 as well as letrozole and fulvestrant if needed, prior to enrollment of the first patient.

5.3.1. Dosage Form(s) and Packaging

5.3.1.1. PF-06873600

PF-06873600 will be provided as tablets for oral administration. The 5 mg, and 25 mg immediate release tablets and the 10 mg and 40 mg MR tablets will be supplied in separate bottles and labeled according to local regulatory requirements. PF-06873600 immediate release tablets are supplied in 68-count bottles, modified release tablets are supplied in 62-count bottles.

5.3.1.2. Letrozole

Letrozole will be supplied by Pfizer. Letrozole is available as 2.5 mg tablets in a 30-count bottle or a 28 count blister pack. Detailed information about letrozole can be found in the approved package insert.

5.3.1.3. Fulvestrant

Fulvestrant (Faslodex[®]) will be supplied by Pfizer. Fulvestrant is available as two 5-mL clear neutral glass (Type 1) barrels, each containing 250 mg/5 mL of fulvestrant solution for intramuscular injection and fitted with a tamper evident closure. The syringes are presented in a tray with polystyrene plunger rod and safety needles (SafetyGlide[™]) for connection to the barrel.

Refer to the local package insert fulvestrant (Faslodex[®]) for instructions and steps necessary for drug preparation and administration. Drug preparation and administration will be performed at the site by a physician, registered nurse, or other qualified health care provider.

5.3.2. Preparation and Dispensing

Only qualified personnel who are familiar with procedures that minimize undue exposure to them and to the environment should undertake the preparation, handling, and safe disposal of chemotherapeutic agents. Refer to package inserts for commercial product preparation and storage.

The study treatment should be dispensed at each visit per the schedule of treatment. A qualified staff member will dispense the investigational product in the bottles provided, in

quantities appropriate for the study visit schedule. The patient/caregiver should be instructed to maintain the product in the bottle provided throughout the course of dosing, keep the investigational product away from children, and return the bottle to the site at the next study visit.

Dose adjustments or discontinuations should be managed according to the [Section 5.4.3](#) below. However, per the investigator's discretion, other dose adjustments may be discussed with the Sponsor.

Any unused product or waste material should be disposed of in accordance with local requirements.

5.4. Administration

5.4.1. PF-06873600

Patients will swallow the investigational product whole, and will not manipulate or chew the investigational product prior to swallowing.

PF-06873600 will initially be administered orally BID on a continuous basis. If supported by emerging data, the QD continuous regimen or alternative intermittent dosing regimen may be considered. A cycle is defined as 28 days, regardless of missed doses or dose delays.

The dosing intervals are as follows:

- For the QD dosing regimen, the single dose should be administered in 24 ±4 hour intervals (ie, no less than 20 hours and no more than 28 hours apart);
- For the BID dosing regimen, the doses should be administered in 12 ±4 hour intervals (ie, no less than 8 hours and no more than 16 hours apart);

PF-06873600 will be administered orally on an empty stomach without adjustment for body size at every cycle. Patients should be instructed to take their medication at approximately the same time each day and to not take more than the prescribed dose at any time. If a patient misses a dose or day of treatment, she or he must be instructed not to “make it up” (unless it was less than 4 hours since their planned dosing time) and to resume subsequent doses the next scheduled time as prescribed. In addition, if a patient vomits any time after taking a dose; she or he must be instructed not to “make it up” but to resume subsequent doses the next day as prescribed. Lastly, if a patient inadvertently takes 1 extra dose during a day, the patient should not take the next dose of PF-06873600.

Letrozole

Letrozole will be administered orally once daily continuously together with PF-06873600. Refer to the package insert for additional administration instructions.

No dose adjustment for letrozole is permitted but dosing interruptions are allowed. Treatment interruption for letrozole-related toxicities will be performed as per the investigator's best medical judgment.

Fulvestrant

Fulvestrant 500 mg will be administered intramuscularly into the buttocks slowly (1-2 minutes per injection) as two 5 mL injections, one in each buttock. Drug preparation and administration will be performed at the site by a physician, registered nurse or other qualified health care provider. Refer to the local product label for Faslodex[®] for detailed administration instructions.

No dose adjustment for fulvestrant is permitted. A single fulvestrant injection can be skipped in case of a fulvestrant-related toxicity or dosing can be delayed. Treatment delay for fulvestrant-related toxicities will be performed as per the investigator's best medical judgment, but by no more than 7 days. If a delay of longer than 7 days is required then the dose should be skipped. In the event of a toxicity requiring dosing delay of PF-06873600, fulvestrant can also be delayed by a maximum of 7 days. Fulvestrant should not be administered if the platelet count is $<50,000/\text{mm}^3$.

5.4.2. Food Requirements

5.4.2.1. Food Requirements

Oral PF-06873600 will be administered with at least 8 ounces (240 mL) of water on an empty stomach. No food or liquids other than water will be consumed for 2 hours before and 1 hour following each dose throughout the study for BID dosing. No food or liquids other than water will be consumed for 2 hours before and 2 hours following each dose throughout the study for QD dosing. These fasting requirements may be removed (via a letter to the investigators) if the data from the food-effect study indicate that there is no meaningful effect of food on the bioavailability of PF-06873600.

5.4.3. Recommended Dose Modifications

Every effort should be made to administer investigational product on the planned dose and schedule.

In the event of significant toxicity, dosing may be delayed and/or reduced as described below. In the event of multiple toxicities, dose modification should be based on the worst toxicity observed. Patients are to be instructed to notify investigators at the first occurrence of any adverse symptom.

Dose modifications may occur in one of three ways:

- Within a cycle: dosing interruption until adequate recovery and dose reduction, if required, during a given treatment cycle;

- Between cycles: next cycle administration may be delayed due to persisting toxicity when a new cycle is due to start;
- In the next cycle: dose reduction may be required in a subsequent cycle based on toxicity experienced in the previous cycle.

5.4.3.1. Dosing Interruptions

Patients experiencing the following adverse events should have their treatment interrupted:

- DLT in Cycle 1 (DLT observation period of 28 days [see [Section 3.1.6](#)]);
- AEs meeting DLT criteria after the DLT observation period.

Appropriate follow-up assessments should be done until adequate recovery occurs as assessed by the investigator. Criteria required before treatment can resume are described in the [Dose Delays](#) section.

Doses may be held as needed until toxicity resolution. Depending on when the adverse event resolved, a treatment interruption may lead to the patient missing all subsequent planned doses within that same cycle or even to delay the initiation of the subsequent cycle.

If the adverse event that led to the treatment interruption recovers within the same cycle, then re-dosing in that cycle is allowed. Doses omitted for toxicity are not replaced within the same cycle. The need for a dose reduction at the time of treatment resumption should be based on the criteria defined in the [Dose Reductions](#) section, unless expressly agreed otherwise following discussion between the investigator and the sponsor. If a dose reduction is applied in the same cycle, the patient may need to return to the clinic to receive new drug supply.

In the event of a treatment interruption for reasons other than treatment-related toxicity (eg, elective surgery) lasting 4 weeks treatment resumption will be decided in consultation with the sponsor.

5.4.3.2. Dose Interruption of Patients with Presumed or Active COVID-19/SARs-CoV2 Infection

Ongoing patients who have active (confirmed [positive by regulatory authority-approved test] or presumed [test pending/clinical suspicion]) SARS-CoV2 infection, should follow the treatment guidelines:

- For symptomatic patients with active SARS-CoV2 infection, investigational treatment should be delayed for at least 14 days from start of symptoms. This delay is intended to allow resolution of symptoms of SARS-CoV2 infection.
- Prior to restarting treatment, the patient should be afebrile for 72 hours and SARS-CoV2-related symptoms should have recovered to Grade ≤ 1 for a minimum of 72 hours. The sponsor should be informed when restarting treatment.

- Continue to consider potential drug-drug interactions for any concomitant medication administered for treatment of SARS-CoV2 infection.

5.4.3.3. Dose Delays

Re-treatment following treatment interruption for treatment -related toxicity or at the start of any new cycle may not occur until all of the following parameters have been met:

- ANC $\geq 1,000/\text{mm}^3$;
- Platelets count $\geq 50,000/\text{mm}^3$;
- Hemoglobin ≥ 8.0 g/DL;
- Nonhematologic toxicities have returned to baseline or Grade ≤ 1 severity (or, at the investigator's discretion, Grade ≤ 2 if not considered a safety risk for the patient).

If a treatment delay results from worsening of hematologic or biochemical parameters, the frequency of relevant blood tests should be increased as clinically indicated.

If these conditions are met within 2 weeks of treatment interruption or cycle delay, PF-06873600 may be resumed. Refer to the Dose Reductions section for adverse events requiring dose reduction at the time of treatment resumption.

If these conditions are not met, treatment resumption must be delayed up to a maximum of 4 weeks. If patients require discontinuation of PF-06873600 for more than 4 weeks at any time during the study, then study treatment should be permanently discontinued, unless it is for reasons other than treatment -related toxicity or the investigator's benefit/risk assessment suggests otherwise after discussion with the sponsor's medical monitor.

If a treatment interruption continues beyond Day 28 of the current cycle, then the day when PF-06873600 is restarted will be counted as Day 1 of the next cycle but tumor assessment will be maintained relative to Cycle 1 Day 1.

5.4.3.4. Dose Reductions

Following dosing interruption or cycle delay due to toxicity, the PF-06873600 dose may need to be reduced when treatment is resumed.

No specific dose adjustments are recommended for Grade 1/2 treatment -related toxicity. However, investigators should always manage their patients according to their medical judgment based on the particular clinical circumstances.

Dose reduction of PF-06873600 by 1 and, if needed, 2 dose levels, or intermediate dose levels, will be allowed depending on the type and severity of toxicity encountered. Patients requiring more than 2 dose reductions will be discontinued from the treatment and entered into the follow-up phase, unless otherwise agreed between the investigator and the sponsor.

All dose modifications/adjustments must be clearly documented in the patient's source notes and CRF.

Patients experiencing a DLT may resume dosing at the next lower dose level (if applicable) once adequate recovery is achieved at the discretion of the investigator. No dose reductions are planned for patients experiencing toxicities other than those listed as DLTs. However, patients experiencing recurrent and intolerable toxicity that does not meet the criteria for DLT (ie, recurrent transient high grade neutropenia or diarrhea) or are Grade 2 may resume dosing at the next lower dose level once recovery to Grade ≤ 1 or baseline is achieved.

Dose reductions during the DLT observation period are not permitted unless the patient experiences a DLT. However, at the discretion of the investigator or sponsor based on emerging safety data, patients may be asked to reduce their dose within the DLT window.

Recommended dose reductions for Part 1 and Part 2 are described in Table 3.

Table 3. Dose Modifications for PF-06873600-Related Toxicity

Toxicity	Grade 1	Grade 2*	Grade 3**	Grade 4
Nonhematologic	Continue at the same dose level.	Continue at the same dose level.	Withhold dose until toxicity is Grade ≤ 1 , or has returned to baseline, then resume treatment at the same dose level or reduce the dose by 1 level at the discretion of the investigator.	Withhold dose until toxicity is Grade ≤ 1 , or has returned to baseline, then reduce the dose by 1 level and resume treatment, or discontinue at the discretion of the investigator.***
Hematologic	Continue at the same dose level.	Continue at the same dose level.	Withhold dose until toxicity is Grade ≤ 2 , or has returned to baseline, then resume treatment at the same dose level. Reduce the dose by 1 level if recurrent or prolonged Grade 3 hematologic toxicity ***	Withhold dose until toxicity is Grade ≤ 2 , or has returned to baseline, then reduce the dose by 1 level and resume treatment. Reduce the dose to 15 mg BID if Grade 4 neutropenia***

*For recurrent and intolerable toxicity that does not meet DLT criteria or Grade 2, see language above.

**Nausea, vomiting, or diarrhea must persist at Grade 3 despite optimal supportive care to require dose modification.

Thrombocytopenia must be Grade 3 with Grade ≥ 2 bleeding to require dose modification.

For QTcF ≥ 501 msec, refer to [Section 7.1.5](#).

***Cycle will not be extended to cover for the missing doses.

Note: Patients with confirmed Hy's Law, must be discontinued.

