3.1.6. DLT Definition

Severity of adverse events (AEs) will be graded according to Common Terminology Criteria for Adverse Events (CTCAE) version 4.03. For the purpose of dose escalation/finding, any of the following AEs occurring in the first cycle of treatment (28 days) which are attributable to one, the other, or both agents in the combination will be classified as DLTs:

Hematologic

- Grade 4 neutropenia lasting >7 days;
- Febrile neutropenia defined as an absolute neutrophil count (ANC) <1.0 x 10⁹/L with a single temperature of >38.3°C, or 101°F, or a sustained temperature of ≥38°C, or 100.4°F, for more than one hour;
 - Grade ≥3 neutropenia with associated infection;
- Grade 3 thrombocytopenia with clinically significant bleeding as indicated by ≥ Grade 2 bleeding;
 - Grade 4 thrombocytopenia.

Nonhematologic:

- Confirmed case of DILI (Hy's Law) as per [Section 8.4.1](#).
- Grade ≥3 AEs that are clinically significant with the following exceptions:
 - Grade 3 nausea, vomiting, or diarrhea for ≥72 hours despite optimal supportive care will be considered a DLT;
 - Grade 3 fatigue for ≥5 days will be considered a DLT;
 - Grade 5 event unless attributed to a cause clearly not related to study treatment.

All DLTs need to represent a clinically significant shift from baseline.

Isolated Grade 3 laboratory abnormalities that are not associated with clinical sequelae or are corrected with supplementation/appropriate management, if indicated, within 72 hours of onset will not be adjudicated as DLTs. However, isolated Grade 4 laboratory abnormalities that are clinically significant will be considered as DLTs. Abnormal objective test findings should be reported as AEs as per [Section 8.2.2](#).

Significant adverse events considered to be related to the investigational product for treatment under investigation that occur during the DLT observation period in the MR Selection Cohort will be reviewed in context of all safety data available. That review may involve re-evaluation of the dosing level or regimen.

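### Protocol Section 5.4.3 and its Table 3 give conflicting dose-reduction and restart instructions, most clearly for Grade 4 neutropenia

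*Protocol*

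**What the plan says.** The instructions sit in three places.

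- **Table 3 (Protocol 5.4.3.4).** Its scope is set by "Recommended dose reductions for Part 1 and Part 2 are described in Table 3", and Protocol 3.2 allows either IR or MR in Part 2. The Grade 4 hematologic cell asks for dosing to be withheld until Grade 2 or lower, "or has returned to baseline, then reduce the dose by 1 level and resume treatment. Reduce the dose to 15 mg BID" in the case of Grade 4 neutropenia; its last sentence reads "Reduce the dose to 15 mg BID if Grade 4 neutropenia". The Grade 3 hematologic cell has the same restart grade, with a one-level reduction if the toxicity recurs or is prolonged. The Grade 3 and Grade 4 nonhematologic cells require Grade 1 or lower, or baseline, before restart.
- **Text of Protocol 5.4.3.4.** "No dose reductions are planned for patients experiencing toxicities other than those listed as DLTs". The exception begins "However, patients experiencing recurrent and intolerable toxicity that does not meet the criteria for DLT", gives recurrent transient high-grade neutropenia as an example, and also mentions Grade 2 toxicity. Such patients may restart one level lower after recovery to Grade 1 or lower, or baseline. Reductions inside the DLT window are ruled out without a DLT, subject to investigator or sponsor discretion.
- **Protocol 5.4.3.3.** Nonhematologic toxicity must return to baseline or Grade 1 or lower, or to Grade 2 at the investigator's discretion "if not considered a safety risk for the patient".

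Two other sections matter. The hematologic DLT list in Protocol 3.1.6 includes "Grade 4 neutropenia lasting >7 days", so a shorter episode without fever or infection is not on it. Protocol 5.3.1.1 lists the supply: "The 5 mg, and 25 mg immediate release tablets and the 10 mg and 40 mg MR tablets will be supplied in separate bottles". Section 5.4.1 has tablets swallowed whole.

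**The concern.** A site facing a Grade 4 neutropenia can find three different instructions within one section, with nothing to say which governs. Restart after other toxicities has a similar problem. Two sites that each follow the protocol could then give different doses after the same event. That matters for patients first. It also matters for the analysis: SAP 9.2.4 tabulates dose reductions, interruptions, their reasons and cumulative dose by dose level, and differences in how sites read the rule would show up there as differences in tolerability. In Part 1 the question also touches the DLT window, because the text generally bars reductions there without a DLT and Table 3 carries no such limit. The rule remains in use, since Appendix 8 continues dosing under Section 5.4 until the end of the trial.

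**Working it through.** The plan states no figure to reproduce. The check is a comparison of passages, with a little arithmetic on the fixed dose.

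**1. The two sentences in the Grade 4 hematologic cell.** Inputs: the monotherapy RDE is 25 mg IR (Appendix 7.1, taken as BID because that cohort is dosed BID); tablet strengths are IR 5 and 25 mg, MR 10 and 40 mg (5.3.1.1); Table 2 names 1, 2, 5 and 10 mg BID and leaves dose level 5 and beyond without a figure.

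- From 25 mg to 15 mg: (25 − 15)/25 = 40% reduction.
- From IR tablets: 3 × 5 mg = 15 mg, so it can be made.
- From MR tablets: any whole-tablet dose is 10a + 40b = 10(a + 4b), a multiple of 10. 15 is not, so it cannot be made.
- One level below 25 mg is not fixed by the documents. If only the named Table 2 levels counted (an assumption), it would be 10 mg, and (25 − 10)/25 = 60%. Intermediate levels are allowed, so other values are possible. The two sentences agree only if 15 mg is the level below 25 mg, and no table says so.
- For a patient already at 15 mg BID with another Grade 4 neutropenia, the first sentence reduces the dose and the second leaves it unchanged.

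**2. A first Grade 4 neutropenia of 7 days or less, without fever or infection.**

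| Source | Instruction |
|---|---|
| 3.1.6, hematologic list | Not listed as a DLT |
| 5.4.3.4 text | No reduction planned; inside the DLT window generally not permitted |
| Table 3, Grade 4 hematologic, first sentence | Reduce by one level |
| Table 3, same cell, second sentence | 15 mg BID |

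The text's exceptions do not reach this case: a first episode is not recurrent, and it is not Grade 2.

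**3. Restart grade.**

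| Event | One place | Another place |
|---|---|---|
| Nonhematologic, Grade 3 or 4 | 5.4.3.3: Grade 2 acceptable by discretion | Table 3: Grade 1 or lower, or baseline |
| Recurrent high-grade neutropenia, not a DLT | 5.4.3.4 text: Grade 1 or lower, or baseline | Table 3 hematologic row: Grade 2 or lower, or baseline |

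Section 5.4.3.1 sends sites to 5.4.3.3 for resumption criteria and to 5.4.3.4 for the need to reduce. It gives no order of precedence for restart where the two differ.

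**The case against.** The best defence of the Grade 4 cell is that a specific rule follows a general one: one level down for Grade 4 hematologic toxicity, and 15 mg BID for neutropenia in particular. Intermediate levels are allowed, so 15 mg need not appear in Table 2, and at 25 mg IR the sentence works. That is a natural reading, but the cell does not state it, and it fails for MR tablets and for patients at or below 15 mg BID.

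On the text and table, Section 5.4.3 and Table 3 are framed as recommendations, and departures may be agreed with the sponsor. Section 3.1.6 also counts clinically significant isolated Grade 4 laboratory abnormalities as DLTs, so some short episodes could qualify by judgment. This softens the conflict but does not settle the ordinary case. A Table 3 footnote refers recurrent and intolerable toxicity back to the text, but its marker sits on the Grade 2 column, and the Grade 3 hematologic cell has its own rule for recurrence.

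On restart, a site could satisfy every passage by taking the strictest. That is true, but nothing tells it to, and the discretion in 5.4.3.3 then has no effect for Grade 3 and 4 events.

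A reader might go further and set 15 mg against the Table 2 levels, inferring that the cell raises the dose by 1.5 to 15 times (15/10 to 15/1). The documents do not support this. The instruction is to reduce, so for a patient below 15 mg BID it is inapplicable rather than an order to escalate. Table 2 gives initial dose levels, and 1 mg and 2 mg cannot be made from the IR strengths now listed. The 25 mg IR RDE is a documented dose from which 15 mg is a true reduction.

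**Conclusion.** The passages conflict and need reconciling. The firmest part is the first short Grade 4 neutropenia, where the text plans no reduction and Table 3 calls for one in two different forms. The missing starting dose, formulation and precedence for the 15 mg sentence are a clear gap, and the MR tablet arithmetic is exact. The restart differences are real, though a cautious site could work around them.

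The size is modest and cannot be expressed as a count, because the documents do not show how many patients had such events, at which dose or on which formulation. The 40% figure assumes the 25 mg IR RDE is given BID.

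A reader might also infer that dose-reduction counts become uninterpretable across sites. They do not. SAP 9.2.4 defines a reduction by the administered against the planned total daily dose, whatever rule prompted it, and lists dosing periods with reasons for change. SAP 9.1 plans no formal hypothesis tests. What remains is avoidable heterogeneity in why and when doses were changed. This is an internal inconsistency in the protocol, not a questionable design choice.

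**What to change.** Reconcile Section 5.4.3.3, the text of 5.4.3.4 and Table 3 so that each toxicity, grade, starting dose and formulation has a single instruction. In particular:

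- state whether the fixed-dose sentence replaces the one-level reduction, and to which starting doses and formulations it applies;
- say what applies to MR patients and to patients already at or below that dose;
- align the text and Table 3 for Grade 4 neutropenia that is not a DLT, including inside the DLT window;
- use one restart grade per situation, or state which section takes precedence.

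Which rule to adopt is for the sponsor's clinical team, and none is proposed here. The cost is a protocol clarification, with no effect on sample size or on the planned analyses.
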